## LIST OF ABBREVIATIONS AND SYMBOLS

ADE	adverse device effect
AE	adverse event
ALT	alanine transaminase
AST	aspartate aminotransferase
BMI	body mass index
°C	degree Celsius
Ca	calcium
CBC	complete blood count
Cl	chloride
CIP	Clinical Investigation Plan
cm	centimetre
CPT	cell preparation tube
CRF	case report form
EC	ethics committee
EDTA	diaminoethanetetraacetic acid
e.g.	for example
et al	and others
g	Gram
GCP	Good Clinical Practice
HPLC	High Performance Liquid Chromatography
lbs	pounds
ICH	International Conference of Harmonization
IEC	Independent Ethics Committee
IRB	Institutional Review Board
K	potassium
kg	kilogram
L	Litre
m	metre
mg	milligram
Mg	magnesium
mL	millilitre
MVM	multivitamin or mineral
Na	Sodium
NHANES	National Health and Nutrition Examination Survey
PBS	phosphate buffer saline
RBC	red blood cells
RCF	relative centrifugal force
RPM	revolutions per minute
SAE	serious adverse event
SOP	standard operating procedure
SST	serum separating tube

TPD Therapeutic Products Directorate  
WBC white blood cell

## 1 INTRODUCTION

According to the National Health and Nutrition Examination Survey (NHANES), approximately 40% of all adults and 31% of children have been found to take multivitamin or mineral supplements (MVM) (1;2). Moreover, 71% of dietary supplement consumers have reported routinely taking a MVM in a recent panel of nationally representative surveys of adults in the United States from 2007 to 2011 (3). Aside from MVM, vitamin C (32%) is also commonly consumed by supplement users who eat a balanced diet and follow a lifestyle routine that is associated with good health (3).

Vitamin C is frequently reported to be below the estimated average requirements for vitamins obtained through dietary sources (2). Moreover, adequate levels of vitamin C are vital for the maintenance of numerous biological functions within the body.

Vitamin C (Ascorbic acid) is an essential water-soluble vitamin in humans, which can be obtained through the diet mainly through fruits and vegetables (4). This nutrient plays an important role as a cofactor for various biological processes, an anti-oxidant, and it provides support for the immune system (5). Pharmacokinetic studies have found that vitamin C has a relatively short plasma half-life that can range from 30 minutes to 8 hours (6). Moyad et al (2008) found that vitamin C accumulates in leukocytes following an acute oral dose of either calcium ascorbate with calcium threonate, or with ascorbic acid alone (7).

While people perceive taking MVM supplements as a healthy lifestyle choice, bioequivalence studies centered on gummy vitamin C formulations are lacking. This may be due to the difficulty in having two competing vitamin products with similar micro-nutrient profiles. This current randomized, examiner-blind, cross-over study will evaluate the bioequivalence of a gummy containing vitamin C relative to a caplet comparator product in healthy adults.

## 2 STUDY OBJECTIVES

The objective of this exploratory pharmacokinetic research study is to demonstrate that both caplets and gummies provide an effective dose of ascorbic acid on healthy adults.

### **Outcomes:**

[figure not shown]
1. The vitamin C  $AUC_{0-24h}$  of the gummy formulation and that of a caplet comparator product
2. The vitamin C  $C_{max}$  of the gummy formulation and that of a caplet comparator product
3. The vitamin C  $T_{max}$  of the gummy formulation and that of a caplet comparator product
4. The vitamin C AUC to infinity ( $AUC_i$ ) of the gummy formulation and that of a caplet comparator product
5. The vitamin C  $AUC_{0-24h} / AUC_i$  of the gummy formulation and that of a caplet comparator product
6. The vitamin C terminal disposition rate constant ( $\lambda$ ) of the gummy formulation and that of a caplet comparator product
7. The vitamin C terminal half-life ( $t_{1/2}$ ) of the gummy formulation and that of a caplet comparator product

### **Safety outcomes:**

1. The difference in vital signs, hematology and clinical chemistry parameters between the gummy formulation vs. that of a comparator product
2. The difference in the incidence of adverse events between the gummy formulation vs. that of a caplet comparator product

### 3 STUDY DESIGN

This will be a randomized, examiner-blind, cross-over, comparator-controlled bioequivalence study.

The planned sample size for this study is 30 participants to complete (equal number of males and females). Assuming 20% drop-out rate from enrollment to completion, 36 participants will be randomized equally to each of the two study arms in an examiner-blind manner at a ratio of 1:1.

Study Arm	Participant Number*
Gummy → Comparator	N = 18
Comparator → Gummy	N = 18
Total	N = 36

\*Assumed 20% drop-out rate from enrollment to completion

To evaluate study outcomes, assessments will be conducted at screening, baseline and, all study visits.

The study will be conducted at a single site in KGK Synergize, [REDACTED].

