## 4 SELECTION OF STUDY POPULATION

This exploratory research study will include 30 healthy male and female participants. Each participant must fulfill the inclusion criteria and not meet any of the exclusion criteria as described in sections 4.1 and 4.2 respectively.

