### 8.3 Analysis Plan

The primary outcome variable will be the peak plasma ascorbic acid level ( $C_{MAX}$ ). The responses from all time points will be compared to determine the time at which the plasma ascorbic acid level reaches its peak ( $T_{MAX}$ ). For each product, a one sample t-test will be utilized to test whether the mean peak plasma ascorbic acid level is greater than 37  $\mu\text{M}$ .

$$H_0: C_{MAX} \leq 37 \mu\text{M}$$

$$H_A: C_{MAX} > 37 \mu\text{M}$$

Because the plasma ascorbic acid level reaches a saturation point at approximately 80  $\mu\text{M}$  (9;10), some of the participants may reach saturation at the peak time. Depending on the proportion of participants who peak at saturation level, a one sample t-test may be inappropriate and nonparametric techniques may be required to judge the typical peak plasma ascorbic acid level for each product.

The action standard for each product will be that the typical peak plasma ascorbic acid level is statistically significantly greater than 37  $\mu\text{M}$  and each product which meets the action standard will be determined to have provided an effective dose.

Additional outcome variables which will be measured include the ascorbic acid level in white blood cells and the ascorbic acid level in urine. These data will be collected for informational purposes only.

Descriptive statistics will be provided for participant demographic and baseline characteristics. Line graphs showing the individual and mean concentrations in  $\mu\text{M}$  of plasma, WBC and urine ascorbic acid over the 24 h will be provided for the investigational products.

Pharmacokinetic parameters, including the incremental area under the curve (iAUC0-24h and iAUC0-∞), the maximum observed concentration (Cmax) time, and maximum concentration (Tmax) will be calculated for each participant. The area under the curve parameter will be calculated using the trapezoid approximation from 0h to 24h and by using the exponential decay approximation for 24h to infinity.

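### The protocol calls the trial a bioequivalence cross-over, but the analysis plan contains no comparison of gummy with caplet

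*Combined protocol and SAP*

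**What the plan says.** The document describes the purpose of the trial in two ways.

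- **Comparative.** Section 1 says the "cross-over study will evaluate the bioequivalence of a gummy containing vitamin C relative to a caplet comparator product in healthy adults". Section 3 gives the formal design: "This will be a randomized, examiner-blind, cross-over, comparator-controlled bioequivalence study".
- **Per product.** Section 2 reads: "The objective of this exploratory pharmacokinetic research study is to demonstrate that both caplets and gummies provide an effective dose of ascorbic acid". It makes no claim about one product relative to the other.

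Section 8.3 follows Section 2. The primary variable is Cmax. "For each product, a one sample t-test will be utilized to test whether the mean peak plasma ascorbic acid level is greater than 37" µM, and "each product which meets the action standard will be determined to have provided an effective dose". If many participants peak at saturation, a nonparametric method may replace the t-test, still product by product.

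The other pharmacokinetic parameters are computed for each participant ("The area under the curve parameter will be calculated using the trapezoid approximation from 0h to 24h", with an exponential extrapolation beyond that), and concentrations are plotted by product. White-cell and urine levels are informational only.

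Section 8.1 calls the trial a pilot with no sample-size calculation. Section 4 also describes it as exploratory: "This exploratory research study will include 30 healthy male and female participants".

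**The concern.** A bioequivalence evaluation estimates one product relative to another and judges the estimate against limits. A one-sample test of the gummy against a fixed 37 µM never uses the caplet data, and the reverse holds for the caplet. The plan can therefore be followed to the letter and leave the question in Sections 1 and 3 unanswered.

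Two things are at stake. First, a report from a self-described bioequivalence study in which both products pass could be read as showing that they are equivalent, which the tests cannot support. Second, every participant takes both products in randomized order, so the data for a within-person comparison will exist. With nothing prespecified, any comparison made later is post hoc: the endpoint, scale, limits and baseline handling could all be chosen after seeing the results.

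**Working it through.** **1. Search for a comparison.** The finding itself needs no arithmetic.

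| Place | Content | Gummy/caplet estimate? |
|---|---|---|
| Section 1 | Says bioequivalence will be evaluated | Promised |
| Section 3 | Design labelled bioequivalence | Promised |
| Section 2, objective | Both products give an effective dose | No |
| Section 2, outcomes | Seven PK parameters for the gummy and for the caplet, listed in parallel | Not defined |
| Section 2, safety outcomes | Worded as differences between products | Not defined |
| Section 8.3, test and fallback | Each product against 37 µM | No |
| Section 8.3, other PK | Computed per participant; graphs by product | No |
| Section 8.3.2 | Descriptive safety tables | No |

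No ratio, difference, interval, equivalence limit, or product/period/sequence model appears anywhere.

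**2. Can two passes coexist with a real difference?** The following is illustration only. From the documents: threshold 37 µM, 30 completers, saturation near 80 µM. Assumed, because the documents give none: true means 50 µM (gummy) and 66.7 µM (caplet), so 50/66.7 = 0.75; SD 15, 20 or 25 µM; one-sided alpha 0.05 or 0.025.

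The pass probability is P(T > t critical), with T non-central t on 29 df and non-centrality (mean − 37)/(SD/√30). For the gummy at SD 20: 13/(20/5.477) = 3.56.

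| SD (µM) | Gummy, 0.05 | Gummy, 0.025 | Caplet, either alpha |
|---|---|---|---|
| 15 | 0.999 | 0.996 | 1.00 |
| 20 | 0.97 | 0.93 | 1.00 |
| 25 | 0.87 | 0.79 | 1.00 |

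**3. What would a paired comparison show?** Assume limits 0.80–1.25, a 90% CI, and within-person CV of 15–40%. On the log scale s_w = √ln(1 + CV²) and SE = s_w·√(2/30), with 28 df. At CV 30%, s_w = 0.294 and SE = 0.076. Treat 0.75 as the geometric mean ratio. The probability that the CI lies inside the limits comes from integrating over the chi-square distribution of the residual variance; the probability that it lies wholly below 0.80 comes from the non-central t.

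| CV | Ratio 0.75: CI inside limits | Ratio 0.75: CI wholly below 0.80 | Ratio 0.95: CI inside limits |
|---|---|---|---|
| 15% | 0.001 | 0.50 | 0.997 |
| 20% | 0.002 | 0.34 | 0.95 |
| 25% | 0.004 | 0.26 | 0.83 |
| 30% | 0.007 | 0.21 | 0.69 |
| 35% | 0.009 | 0.18 | 0.52 |
| 40% | 0.011 | 0.16 | 0.37 |

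The 0.95 column is a convenient reference: the dose tolerance in Section 5.5 allows at the extreme 975/1025 = 0.951.

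**4. Effect of saturation.** Section 8.3 warns: "Because the plasma ascorbic acid level reaches a saturation point at approximately 80" µM. With normal values hard-capped at 80 µM, the expected means at SD 15, 20 and 25 become 49.9/65.2, 49.4/63.7 and 48.6/62.0, giving ratios of about 0.77, 0.78 and 0.78. The ceiling narrows the Cmax gap without closing it.

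**5. Can product and period be separated?** In Appendix 5, after dropping the two unused numbers from each list, the first 18 numbers give 9 A-first and 9 B-first in each sex, so they can.

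**The case against.** The strongest reply is that Section 2 holds the only stated objective, and Section 8.3 tests exactly that and concludes no more. On this reading bioequivalence is a stray label in the background and design text, the study is an exploratory pilot, and a wording change would cure it. The Section 2 outcomes list also sets gummy and caplet values side by side, not as a ratio or difference, which suits per-product reporting.

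Much of this stands. No confirmatory equivalence claim is owed, and the primary test and action standard are unaffected. But Section 3 is the formal design statement, Section 1 says what the study will do, the safety outcomes are worded as differences, and the document never says which description governs. Pilot status removes the need for confirmatory power, not the need to say how a stated question will be estimated. Graphs by product give neither a within-person ratio nor its uncertainty.

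A second objection is that the illustration rests on assumed figures and ignores the ceiling in its main tables. That is fair: at SD 15, 20 and 25 µM about 19%, 25% and 30% of uncapped caplet values would exceed 80 µM, although the mean is below it. Linking a Cmax ratio of 0.95 to the dose tolerance also assumes that Cmax is proportional to dose, which saturation makes doubtful. The capped ratios of 0.77–0.78 show that the point survives, and the finding does not depend on any of these numbers.

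**Conclusion.** The concern holds. Sections 1 and 3 state a comparative question that Section 8.3 cannot answer, because its only hypothesis test judges each product alone. This follows from the text and needs no assumption.

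Its weight is moderate: it should be fixed, but the effective-dose conclusion is not endangered. In the illustration, both products would usually be called effective while the gummy's mean Cmax is 25% lower (about 22–23% lower under a hard cap at 80 µM); a paired 90% CI would then fall inside 0.80–1.25 with probability of at most 0.011. Means, SDs, CVs, alpha and limits are assumed, and the cross-over figures assume no ceiling.

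A comparison would have limits of its own. A true ratio of 0.75 would usually give an inconclusive interval, and power to show equivalence at 0.95 falls below 0.70 once the CV reaches 30%. The data would support an estimate with its uncertainty, not necessarily a firm answer.

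**What to change.** Choose one of two routes.

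**Add the comparison (preferred).** In Section 8.3, prespecify an exploratory model for log AUC0-24h and log Cmax with product, period and sequence as fixed effects and participant as random. Report the gummy/caplet geometric mean ratio with a 90% CI against pre-stated limits, for example 0.80–1.25. State that no confirmatory claim follows, since no sample size was calculated. Also state:

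- how baseline is handled. Section 8.3 plans incremental AUC, and a zero or negative value has no logarithm. One option is to model uncorrected AUC0-24h with that period's 0 h concentration as covariate and show iAUC as a sensitivity analysis;
- the analysis population, since the per-protocol set in Section 8.2 keeps completers only;
- that Cmax is to be read together with AUC because of the expected saturation;
- that passing both 37 µM tests supports no equivalence claim.

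Align the wording of Sections 1 and 3 with Section 2.

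**Or drop the claim.** Remove the bioequivalence wording from Sections 1 and 3.

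**Cost.** No new visits, samples or participants. The first route takes one extra model per endpoint. Either takes a protocol amendment, which under Section 6.11 may need IRB and Health Canada review. The price of the first route is that the result may be inconclusive.

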## 4 SELECTION OF STUDY POPULATION

This exploratory research study will include 30 healthy male and female participants. Each participant must fulfill the inclusion criteria and not meet any of the exclusion criteria as described in sections 4.1 and 4.2 respectively.

### 4.1 Inclusion Criteria

1. Healthy male or female from 18 and 55 years of age inclusive.
2. If female, participant is not of child bearing potential, which is defined as females who have had a hysterectomy or oophorectomy, bilateral tubal ligation or are post-menopausal (natural or surgically with > 1 year since last menstruation)  
OR  
Females of childbearing potential must agree to use a medically approved method of birth control and have a negative urine pregnancy test result. A minimum of 3-months stable dose is required for females on a hormonal birth control. Acceptable methods of birth control include:
  - Hormonal contraceptives including oral contraceptives, hormone birth control patch (████████), vaginal contraceptive ring (████████), injectable contraceptives (████████████████), or hormone implant (████████████████)
  - Double-barrier method
  - Intrauterine devices
  - Non-heterosexual lifestyle or agrees to use contraception if planning on changing to heterosexual partner(s)
  - Vasectomy of partner (shown successful as per appropriate follow-up)
3. BMI 18.5 to 29.9 kg/m^2 ( $\pm 1$  kg/m^2)
4. Healthy as determined by laboratory results and medical history
5. Agrees to maintain current level of physical activity throughout the study
6. Agrees not to donate blood for the next 3 months after completing the study
7. Agrees to avoid foods and beverages fortified with vitamin C for at least 7 days prior to enrolment and during the study
8. Agrees to avoid citrus foods, citrus juices (e.g. orange, grapefruit, lemon, lime, orange juice, grapefruit juice and lemonade), and tomato juice for at least 7 days prior to enrolment and during the study
9. Non-smoker or ex-smoker >1 year
10. Has given voluntary, written, informed consent to participate in the study
11. Agrees to avoid high caffeine and alcohol intake 72 hours prior to in-clinic test days and during the 24-hour in-clinic test days

### 4.2 Exclusion Criteria

1. Women who are pregnant, breast feeding, or planning to become pregnant during the trial

2. Duodenal or gastric ulcer, gastritis, hiatus hernia, or GERD within past 3 months
3. History irritable bowel syndrome and related disorders
4. Significant gastrointestinal disease (examples include but are not limited to Celiac disease)
5. History of malabsorption
6. Unstable medical conditions as determined by the Qualified Investigator
7. Blood pressure greater than 150/90 mmHg
8. Cancer except skin cancers completely excised with no chemotherapy or radiation following and with a negative follow up. Volunteers with cancer in full remission for more than 5 years after diagnosis are acceptable.
9. Clinically significant abnormal laboratory results at screening
10. Metabolic disease or chronic diseases (examples include and not limited to hyperlipidemia, hypertension, and hypercholesterolemia)
11. Type I or Type II diabetes
12. History of kidney stones
13. Use of prescription or over the counter products known to interact with vitamin C within 72 hours of enrolment and during the trial such as aspirin and NSAIDs (including acetaminophen containing medications), aluminum (found in most antacids),, iron, and proton pump inhibitors
14. Use of acute over the counter medication within 72 hours of test product dosing
15. Use of tobacco products within the last year
16. More than 2 alcoholic drinks per day
17. Drug abuse within 1 year of enrolment
18. Use of medicinal marijuana
19. Immunocompromised individuals such as individuals that have undergone organ transplantation or individuals diagnosed with human immunodeficiency virus (HIV)
20. Individuals who have planned surgery during the course of the trial
21. St. John's wort in the last 30 days prior to enrolment and during the study
22. Use of vitamin C, multivitamins containing vitamin C, or foods or beverages fortified with vitamin C and other natural health products containing vitamin C within 7 days of enrolment and during the study
23. Consumption of citrus foods, citrus juices (e.g. orange, grapefruit, lemon, lime, orange juice, grapefruit juice and lemonade), and tomato juice within 7 days of enrolment and during the study
24. Use of anticoagulants (warfarin), barbiturates, tetracycline antibiotics, beta-blockers, cyclosporine, prednisone, tricyclic antidepressants, diuretics and nitrate medications (including daily use of low-dose Aspirin)
25. Use of natural health products/dietary supplements within 7 days of enrolment or during the study
26. Current diagnosis and history of blood/bleeding disorders
27. Current diagnosis and history of anemia of any etiology defined as hemoglobin < 145 g/L for males and < 123 g/L for females
28. History of hemoglobinopathies such as sickle cell anemia or thalassemia, sideroblastic anemia

29. History of hemochromatosis
30. Blood donation in the past 3 months
31. Individuals who plan to donate blood during the study or within 30 days of completing the study
32. Participation in a clinical research trial within 30 days prior to enrolment
33. Allergy or sensitivity to supplement ingredients or to any food or beverage provided during the study
34. Individuals who are cognitively impaired and/or who are unable to give informed consent
35. Any other condition which in the Qualified Investigator's opinion may adversely affect an individual's ability to complete the study or its measures or which may pose significant risk to the individual

#### **4.3 Concomitant Medications**

Participants who are currently taking any prescribed medications except for birth control will be excluded from the study.

- Use of natural health products/dietary supplements within 7 days of enrolment or during the study is not permitted.
- Use of acute or over the counter medication within 72 hours of test days is not permitted.
- Consumption of tomato juice, citrus foods, or citrus juice (e.g. orange, orange juice, grapefruit, grapefruit juice, lime, lemon, and lemonade)
- Food and beverages fortified with vitamin C within 7 days of enrolment and during the trial.
- St. John's wort is prohibited 30 days prior to enrolment and during the trial.
- Use of prescription or over the counter product known to interact with vitamin C such as aspirin (including daily use of low-dose Aspirin), NSAIDs (including medications containing acetaminophen), aluminum, iron and proton pump inhibitors are prohibited 72 hours prior to enrolment and during the study.
- Vitamin C or multivitamins containing vitamin C are not allowed within 7 days of enrolment and during the duration of the study.
- The following are prohibited in this study: anticoagulants (warfarin), barbiturates, tetracycline antibiotics, beta-blockers, cyclosporine, prednisone, tricyclic antidepressants, diuretics, nitrate and marijuana.
- Tobacco products are prohibited within 1 year of enrolment and during the study.

#### **4.4 Early Withdrawal**

##### **Personal reasons**

As stated in the Informed Consent Form, a participant may withdraw from the study for any reason at any time.

